2. STUDY OBJECTIVES & ENDPOINTS

2.1 PRIMARY OBJECTIVES

2.1.1 Primary Objective

To determine if, in patients with symptomatic lacunar ischaemic stroke, the routine long-term administration of isosorbide mononitrate 50mg od or equivalent, and /or cilostazol 100mg bd, individually or together, in addition to continuing routine stroke prevention therapy, compared with continuing routine stroke prevention therapy alone, reduces cognitive impairment after lacunar ischaemic stroke, a marker of cerebral small vessel disease.

2.1.2 Primary Endpoint

At 18 months:

• 7-level ordinal cognitive impairment, based on operationalisation of DSM-V criteria of cognitive impairment or dementia derived using subscores of the tMOCA, TICS, animal naming, clinical dementia diagnosis, as in LACI-2 and R4VaD.

2.2 SECONDARY OBJECTIVES

2.2.1 Secondary Objectives

To determine if the long-term administration of isosorbide mononitrate 50mg od or equivalent and/or cilostazol 100mg bd individually or together, in addition to continuing routine stroke prevention therapy, compared with continuing routine stroke prevention therapy alone, reduces dependency, recurrent stroke or TIA, MI, death, and improves mood, quality of life, and health economic resource usage and is safe and well tolerated in long term use in patients with lacunar ischaemic stroke, a marker of cerebral small vessel disease.

2.2.2 Secondary Endpoints

At 18 months:

- dependency (defined as mRS>2)
- tMOCA
- TICS
- Concentration (from MMSE)
- Animal naming
- Recurrent ischaemic stroke or TIA or haemorrhagic stroke
- Fatal or non-fatal MI
- Stroke Impact Scale (individual domains and global)
- EQ5D-5L, EQ-VAS
- Death, due to vascular and any cause;
- Safety SAEs;
- IMP Symptoms (headache; palpitations; loose stools; falls; etc);
- Composite of recurrent stroke or TIA, MI, death, dependency (mRS>2), cognitive impairment.
- Global Clinical Outcome of recurrent stroke or TIA, MI, death, mRS>2, cognitive impairment, QoL, mood (ZUNG)
- Health economic usage

2.3 TERTIARY OBJECTIVES

2.3.1 Tertiary Objectives

To collect data on the antihypertensive drug prescriptions and blood pressure measurements made by participants or available from GP or hospital medical records as a part of the routine stroke prevention therapy.

2.3.2 Tertiary Endpoints

BP measures

3. STUDY DESIGN

LACI-3 will be an investigator-led, Phase III, prospective, randomised, controlled, 2x2 partial factorial, open label, blinded outcome trial performed in multiple UK hospital-based centres. LACI-3 is open to support international collaboration. The trial received Scientific Advice from the Medicines and Health Care Regulatory Agency assisted by NHS England Medicines Repurposing Programme at a meeting on 2nd July 2024. All MHRA guidance has been incorporated into the design of LACI-3.

Duration: The trial will last for 52 months with the treatment phase for each participant starting from within one day of randomisation until the end of trial follow-up at 18 months.

Participants meeting inclusion/exclusion criteria will be randomised at participating hospitals.

Participants will be randomised to start one of four treatments; ISMN only; cilostazol only; both ISMN and cilostazol; or neither ISMN nor cilostazol. Patients with contraindications to cilostazol can be randomised to ISMN versus no ISMN arms only; patients with contraindications to ISMN can be randomised to cilostazol versus no cilostazol arms only. The partial factorial design allows testing of both drugs when given alone and together. As in LACI-2, the doses will be escalated until participants are on their full dose by 1 month. If a patient encounters intolerable side effects at full dose, then they will be able to remain on the highest dose regime that they can tolerate and this dose will be recorded. The total duration of the trial drug administration will be 18 months. After the end of follow-up, the patients will reduce the tablets over about two weeks and then stop the trial medication. They will return any unused drug to their local community pharmacy or the hospital pharmacy if more convenient for destruction.

Drug supply: Trial drug will be dispensed by hospital pharmacies. The first drug supply will be given at the randomisation visit if allocated to the IMP. The IMP re-supply for the followup at 6 and 12 months will be posted to participants. Participants can collect the IMP resupply in person from the recruiting site.

Participants should continue their allocated treatment until the end of 18-month follow-up.

Discontinuing the allocated treatment by the participant's direct clinical care team due to the occurrence of an outcome event does not constitute withdrawal.

Throughout the trial, patients will continue to take their normal prescribed medication which will include guideline stroke secondary prevention prescribed since their event as per national guidelines/usual post-stroke care in participating centres and including lifestyle advice.

Measurement of outcomes: The trial follow-up visits will be done remotely by phone, post or web-based. The outcome measurement after randomisation and from 6 months onwards until the last follow-up at 18 months will be assessed by the local hospital sites teams and the central trial coordinators located in Edinburgh and Nottingham.

Stopping rules for the trial by Data Monitoring Committee:

The trial will not stop unless asked to do so by the Data Monitoring Committee (DMC).

The DMC will review un-blinded data at regular intervals and, in the light of these analyses, will advise the chair of the TSC and Sponsor (via the chief investigator) if, in their view, the randomised comparisons in LACI-3 have provided both (i) "proof beyond reasonable doubt" that for all, or for some, specific types of patient, a LACI-3 treatment is clearly indicated or clearly contraindicated, and (ii) evidence that might reasonably be expected to materially influence future patient management by many clinicians who are already aware of the results of any other relevant trials. Appropriate criteria of 'proof beyond reasonable doubt' cannot be specified precisely.

The stopping rules for effectiveness are based on the combination of presence of 'proof beyond a reasonable doubt' and the likelihood that the results would change clinical practice. The possible DMC recommendations at any assessment are:

1. Stop enrolment if the treatment is negative, i.e. treatment is hazardous: statistical evidence that intracerebral haemorrhage, systemic bleeding, or fatal SAE rates are significantly higher in the ISMN vs no ISMN or cilostazol vs no cilostazol or both vs neither groups (p<0.01), on safety data assessed at any of 6, 12 or 18 months of treatment;

2. Stop enrolment if the study is positive, i.e., treatment is beneficial: the combination of statistical evidence that cognitive function is significantly better in the patients allocated ISMN, or cilostazol, or both, vs not allocated that treatment "beyond reasonable doubt" (i.e. at least 3 standard errors difference in magnitude1) and the overall trial results will lead to a change in clinical practice, e.g. by also taking account of evidence that at least some secondary outcomes are also being benefitted, for example, some of less dependency (mRS), less recurrent stroke, better individual cognitive scale scores, and/or better quality of life.

3. Continue enrolment if the study is neutral: or if conditions 1 and 2 are not present.

4. Modify study design – if it appears that:

i. Sample size calculation assumptions were incorrect, e.g., if OR of cognitive impairment is much less than 0.7;

ii. Apparent study design aspects will lead to incorrect study conclusions;

iii. Specific clinical procedures, e.g. change in usual stroke prevention drugs, might jeopardise the safe execution of the study.

Formal statistical analyses will be used as "stopping guidelines" rather than absolute rules. In the light of interim data, and other evidence from relevant studies (including updated overviews of relevant randomised controlled trials), the DMC will inform the TSC, if in their view there is proof beyond reasonable doubt that the data indicate that the intervention is either clearly indicated or contra-indicated, either for all or for a particular subgroup of study participants. A decision to inform the TSC will in part be based on statistical considerations. Appropriate criteria for proof beyond reasonable doubt are not specified precisely. A difference of at least 3 standard errors in the primary endpoint may be needed to justify halting, or modifying, the study prematurely. This approach has the practical advantage that the exact number of analyses are of little importance, and so no fixed schedule is proposed. The DMC may also consider supporting evidence from secondary outcomes in their decision making, but the overall guidance remains that the results should be sufficiently convincing to change practice.

Stopping rules for the trial by funder:

There will be two trial phases with no break in recruitment unless LACI-3 meets stopping criteria

Table 1 Progression criteria	Red	Amber	Green
% Threshold	≤35%	65%	100%
Trial Recruitment	110	205	300
Recruitment rate/site/month	1.1	1.1	1.1
Number of sites opened	24	35	48
Total number of participants recruited	110	205	300

Table 1: Trial progression criteria – target recruitment rate 1.1pt/site/month

Amber actions 1: Increase recruitment – protocol review, identify/remove barriers, re-train sites, increase recruitment at active sites/close inactive sites, increase number of sites.

Red actions 2: as for amber + acceleration plan as per HTA.

We will review recruitment of sites and participants monthly and commence mitigation measures if it becomes clear that the study is behind schedule.

There will be no break in recruitment between phases unless recommended by the DMC.

Vanguard phase: Recruitment of 300 participants from up to 48 sites by month 12 after recruitment starts (1.1 ppm) which will be 16 months after the grant starts (Figure X). These sites will necessarily include those of the applicants and some larger hospitals with existing LACI trial experience.

Main phase: Recruitment of 900 participants over 32 months from 60 sites, (1.1 p/pm/site) (Figure 1). The expected recruitment rate is slightly lower than in the pilot phase since there will be a higher proportion of lower volume stroke sites. The reason for this difference is to ensure the main protocol works in experienced sites before expanding out to sites where PES-training will be key.

Figure 1: Planned recruitment rate.

The trial flow diagram (Figure 2) summarises the study design:

§ IMP symptoms will be assessed by site after randomisation at 1-2 weeks and 3-4 weeks visits and by the blinded central team at 6, 12 and 18 months; entered in masked section of database.

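### The DMC's numbered recommendations have no harm branch for the primary cognitive outcome, ischaemic stroke/TIA or non-fatal MI, and item 3's default contradicts the two-directional text around it

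*Protocol*

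**What the plan says.** Under the DMC stopping rules in Protocol section 3, four numbered items are presented as the recommendations available at any assessment.

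- **Item 1 (hazardous):** stop enrolment on "statistical evidence that intracerebral haemorrhage, systemic bleeding, or fatal SAE rates are significantly higher in the ISMN vs no ISMN", or for cilostazol versus none, or both versus neither. The threshold is "p<0.01), on safety data assessed at any of 6, 12 or 18 months of treatment".
- **Item 2 (beneficial):** stop enrolment on "the combination of statistical evidence that cognitive function is significantly better in the patients allocated ISMN, or cilostazol, or both", by at least 3 standard errors, together with a judgement that practice would change. Recurrent stroke is mentioned only as a supporting benefit.
- **Item 3:** "Continue enrolment if the study is neutral: or if conditions 1 and 2 are not present".
- **Item 4 (modify):** wrong sample-size assumptions (the example is an odds ratio well below 0.7), design features that would lead to wrong conclusions, or clinical procedures that threaten safe conduct.

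The text before the list asks the DMC to advise when "a LACI-3 treatment is clearly indicated or clearly contraindicated". The text after it asks the DMC to inform the Trial Steering Committee when "the intervention is either clearly indicated or contra-indicated, either for all or for a particular subgroup of study participants". It adds: "A difference of at least 3 standard errors in the primary endpoint may be needed to justify halting, or modifying, the study prematurely". The same paragraph describes the formal analyses as guidelines and not absolute rules, and lets secondary outcomes support a decision.

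Section 10 (Pharmacovigilance) calls a set of secondary outcomes the main factor in assessing the drugs' safety. The set is recurrent ischaemic stroke, TIA, major haemorrhage, fatal or non-fatal MI, death of any cause and dementia. The same section exempts these events from SAE reporting.

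**The concern.** The list is the operational part of the stopping section, and its default branch is explicit. Item 3 covers more than neutral results: after its "or", it covers everything that is not item 1 or item 2. The primary outcome can trigger a recommendation only when it improves. Ischaemic stroke/TIA and non-fatal MI can never trigger the hazard branch.

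A DMC that sees clear cognitive harm would therefore find a numbered recommendation to continue beside prose that would support halting. Stopping guidance should not be ambiguous in that situation, because the trial is open label, has three treatment comparisons and has no fixed schedule of looks.

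Section 10 adds a second gap. Item 1 counts fatal SAEs, but death of any cause is a trial outcome exempt from SAE reporting. Read literally, a count of fatal SAEs could miss most deaths.

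**Working it through.** No stated figure is in dispute, so the main check sets the branches side by side.

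| Result seen by the DMC | Items 1–3 read literally | Surrounding prose in section 3 |
|---|---|---|
| Cognition better by ≥3 SE, practice-changing | Item 2: stop enrolment | Clearly indicated; 3-SE guide met |
| Excess intracerebral or systemic bleeding or fatal SAEs, p<0.01 | Item 1: stop enrolment | Contraindicated |
| Cognition **worse** by ≥3 SE, no excess bleeding or fatal SAEs | Neither item met, so item 3: continue | 3-SE guide met; contraindicated |
| Clear excess of ischaemic stroke/TIA or non-fatal MI only | Neither item met, so item 3: continue | May support a finding of contraindicated |

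The third row is a direct contradiction. In the fourth row the prose permits action and the list does not. Item 4 does not clearly fill the gap: its only numerical example lies in the benefit direction, and none of its three limbs names harm on the primary outcome.

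**How often this could arise during enrolment.** The protocol gives no harm scenario. I assume harm as large as the planned benefit, OR = 1/0.70 = 1.43, and the control distribution in section 9.1 (35/24/12/20/3/3/3%).

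1. Check of inputs. The proportional-odds formula is N = 12(z₁₋α/₂ + z₁₋β)² / [(ln OR)²(1 − Σp³)]. With control Σp³ = 0.0665, ln 0.70 = −0.3567 and z-values 1.960 and 1.282, N = 1062. Allowing for 15% loss gives 1062/0.85 = 1249 or 1062 × 1.15 = 1221. Both are within 3% of the protocol's 1229 at 90% power.
2. Evaluable number. Section 4.1 plans 1300 participants over about 30 months, 300 of them by month 12. When enrolment closes at month 30, only those randomised by month 12 have 18-month data: 300 × 0.85 = 255.
3. Standard error of ln OR = √[12/(N(1 − Σp̄³))]. With arm-averaged proportions at OR 1.43, 1 − Σp̄³ = 0.944. At N = 255, SE = √[12/(255 × 0.944)] = 0.223.
4. Expected Z = 0.3567/0.223 = 1.60. The chance of exceeding 3 SE at that look is P(Z > 3 − 1.60) ≈ 0.08.
5. Range. Section 3 also gives a longer schedule: 300 in 12 months, then 900 in 32 months. With even accrual, those randomised by month 26 number 300 + 900 × 14/32 ≈ 694, or about 590 after 15% loss. Then Z = 1.60 × √(590/255) = 2.43 and the chance is about 0.28.

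**Cost of a symmetric 3-SE guide.** Under no effect, the chance of a result at least 3 SE in the harmful direction is 0.0027/2 = 0.00135 per comparison per look. Across three comparisons it is at most 3 × 0.00135 = 0.004 per look.

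**The case against.** The strongest reply is that the list is not a closed algorithm. The paragraphs before and after it cover both directions, the criteria are expressly left imprecise, the analyses are only guidelines, and secondary outcomes may be weighed. A sensible DMC would not feel bound to continue in the face of cognitive harm. This stands. A reader might infer that the protocol obliges the DMC to keep randomising to a drug shown to worsen cognition, and the documents do not support that.

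Three further limits also stand.

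- A reader might infer that the harm rule ignores recurrent stroke altogether. It does not: intracerebral haemorrhage is an input to item 1, and section 2.2.2 counts haemorrhagic stroke in the recurrent-stroke endpoint. What is missing is ischaemic stroke/TIA and non-fatal MI.
- Larger crossing probabilities can be computed for half or all of the sample, but not that many participants will have 18-month data while an enrolment decision is still open. Cognition is also collected at 6 and 12 months (section 6.9), so an interim look might use more data, but item 2 does not name a time point.
- The DMC charter cited in section 11.3 is not available here and may say more.

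None of this removes the conflict. Guideline status does not say which of two conflicting guides applies, and a charter cannot correct the protocol's own wording.

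**Conclusion.** The point holds as an internal contradiction in section 3. Items 1 to 3 have no harm branch for the primary outcome, ischaemic stroke/TIA or non-fatal MI. Item 3's default literally returns continued enrolment when cognition is clearly worse. The adjoining prose treats the same data as possible grounds for halting, so the two must be reconciled.

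The practical size is modest. For harm as large as the planned benefit, the chance of crossing 3 SE on 18-month data before enrolment closes is about 8% on the section 4.1 schedule and about 28% on the longer schedule in section 3. These figures assume OR 1.43, 15% loss, a single look and, for the second, even accrual. The contradiction itself depends on none of these assumptions.

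**What to change.** In section 3:

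1. State that the existing guide of at least 3 standard errors on the primary endpoint applies in both directions, for each of the three comparisons.
2. Reword item 3 so that continuing enrolment is the recommendation only when there is neither clear benefit nor clear harm.
3. State that vascular outcome events and deaths exempt from SAE reporting under section 10 (including ischaemic stroke, MI and death of any cause) count in the DMC's assessment of harm. Leave any numerical threshold for them to the DMC and sponsor. A fixed significance test for recurrent stroke and MI would be a new rule, and the reconciliation does not need one.

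The cost is a wording amendment and alignment of the DMC charter. No new data are needed, because cognition and vascular events are already collected at 6, 12 and 18 months. The added chance of a false harm signal on cognition is very small, as shown above.

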4. STUDY POPULATION

4.1 NUMBER OF PARTICIPANTS

We aim to recruit 1300 participants, over about 30 months who will be followed up to 18 months. Recruitment will take place in two phases at the request of the funder: a vanguard or 'internal pilot' phase and a 'main' phase. The vanguard phase will be assessed at 16 months after the grant starts, i.e., after 12 months of recruitment, and run seamlessly into the main phase assuming that recruitment is to target (300 patients by 12 months of recruitment).

LACI-3 will include patients who are independent in activities of daily living (modified Rankin ≤2) with symptoms and brain imaging compatible with a recent lacunar ischaemic stroke, aged >30, who can be recruited at least 24 hours after lacunar stroke symptom onset with no latest time limit after the stroke, who have capacity to give consent and no exclusion criteria.

4.2 INCLUSION CRITERIA

Inclusion criteria:

- Age ≥30 years;
- Clinical stroke syndrome compatible with a lacunar stroke and brain imaging (MRI preferred but CT allowed) at the time of the stroke shows a relevant recent small subcortical infarct, or if no relevant infarct then no other explanation for symptoms is seen;
- Genetic forms of SVD (e.g. CADASIL) may be included if they present with a lacunar stroke.
- Capacity to give consent in the opinion of the PI or any delegated member of the research team;

4.3 EXCLUSION CRITERIA

General exclusion criteria:

- Less than 24 hours since onset of the lacunar stroke or patient on dual antiplatelet drugs;
- Stroke mechanism with definite treatment indication (e.g. cardioembolism, ipsilateral carotid stenosis);
- Other explanation for the lacunar stroke symptoms (ie recent cortical infarct, haemorrhage or tumour);
- Other active neurological disease (e.g. brain tumour, multiple sclerosis, recurrent seizures, neurodevelopmental disorder well-controlled epilepsy present prior to the lacunar stroke, a single seizure at onset of the stroke, or provoked seizure, is not an exclusion);
- Contraindication to both trial drugs in section 4.3 of the SPCs (patients with a contraindication to one trial drug may still be randomised to the other trial drug);
- Indication for either trial drug (patient already prescribed one trial drug may still be randomised to the other trial drug);
- Dependent (mRS>2);
- Clinical diagnosis of dementia;
- Planned surgery during the trial period including carotid endarterectomy. Note prior and apparently successful carotid endarterectomy (or other surgery) is not an exclusion criterion and patients who would otherwise be eligible but require endarterectomy first may be randomised after recovery from successful endarterectomy;
- Unable to swallow;
- Diagnosis of hypotension, defined as sitting systolic blood pressure less than 100mmHg;
- History of drug overdose or attempted suicide

- Unlikely to be available for follow-up at 18 months;
- Unlikely to comply with study procedures and follow-up procedures for whatever reason (eg history of poor medication compliance) in the opinion of the randomising physician;
- Pregnant, breast-feeding, or of child-bearing potential and not using highly effective contraception as stated in section 10.9 (Pregnancy);
- Renal impairment (creatinine clearance <25 ml/min)
- Hepatic impairment
- Currently prescribed dual antiplatelet treatment (single antiplatelet is not an exclusion); patients can be randomised into the trial once the 28-day period of dual antiplatelet for guideline secondary prevention following the acute lacunar ischaemic stroke has completed;
- Previously enrolled in LACI-3;
- Enrolled in a study that precludes co-enrolment with LACI-3.

Cilostazol exclusion criteria (still allows randomisation to ISMN):

- Definite indication for (i.e. already prescribed) Cilostazol, or definite contraindication to Cilostazol as per SPCs section 6.1.8.
- Prohibited medications to Cilostazol (see sections 4.5 of the appended SPCs and protocol section 6.7.3).
- Active cardiac disease (atrial fibrillation, myocardial infarction in past 6 months, active angina, symptomatic cardiac failure).
- Bleeding tendency (e.g. known platelets<100, active peptic ulcer, history of intracranial haemorrhage such as subdural haematoma, subarachnoid haemorrhage, intracerebral haemorrhage, but not asymptomatic haemorrhagic transformation of infarction or a few microbleeds, taking anticoagulant medication)

ISMN exclusion criteria (still allows randomisation to Cilostazol):

- Definite indication for (i.e. already prescribed) ISMN, or definite contraindication to ISMN as per SPCs.
- Prohibited medications to ISMN (see sections 4.5 of the appended SPCs and protocol section 6.7.3).

